9.7.1.2 Site(s) Performing Correlative Study

Dana-Farber Cancer Institute

9.7.1.3 Risks of Research Biopsy and Procedures for Minimizing Risk

Potential risks according to site are:

Breast (core biopsy):

- Likely: local discomfort and minor bleeding.
- Less likely: moderate or major bleeding, need for blood transfusion, hospitalization due to bleeding or other complications, infection, pneumothorax, damage to adjacent organs.

Skin/chest wall (punch biopsy):

- Likely: local discomfort and minor bleeding
- Less likely: moderate or major bleeding, or infection

Lymph node, liver, or bone (core needle biopsy):

- Likely: local discomfort and minor bleeding
- Less likely: moderate or major bleeding, need for blood transfusion, hospitalization due to bleeding or other complications, infection, damage to adjacent organs. Additional risks may be present if intravenous conscious sedation is required

Pleural fluid (thoracentesis):

- Likely: local discomfort and minor bleeding
- Less likely: moderate or major bleeding, need for blood transfusion, hospitalization due to bleeding or other complications, infection, pneumothorax, damage to adjacent organs

Ascites fluid (paracentesis):

- Likely: local discomfort and minor bleeding
- Less likely: moderate or major bleeding, need for blood transfusion, hospitalization due to bleeding or other complications, infection, bowel perforation or damage to adjacent organs. In order to minimize the risk of a biopsy, only qualified personnel will perform these procedures.

Prior to the procedure, the physician performing the procedure will discuss the risks with each study participant, answer any questions, and obtain separate procedure consent. Patients will be evaluated for comorbidities or concomitant medications that may increase the risk of potential complications. For biopsies of lesions that are not superficial and clearly palpable, imaging studies such as CT or ultrasound will be used to guide the biopsy in order to minimize the risk of damage to adjacent structures. After lymph node biopsies, patients will be observed a minimum of 2 hours (range 2-4 hours) after the procedure, or according to standard institutional guidelines. After liver biopsies, patients will be observed a minimum of 4 hours (range 4-6 hours) after the procedure, or according to standard institutional guidelines. Less than the goal quantity of tissue is accepted for each type of biopsy, and will be left to the clinical judgment of the physician performing the procedure.

9.7.1.4 Risks of Anesthesia

Local Anesthesia

All biopsy procedures require local anesthesia using lidocaine, xylocaine, or related compounds. There is a small risk of an allergic reaction associated with these drugs. In order to minimize the risk of local anesthesia, only qualified personnel will perform the biopsy procedure. Patients will be queried if they have had previous allergic reactions to local anesthetics.

Intravenous Conscious Sedation

Certain biopsy procedures, such as lymph node, liver, or bone biopsies, may require intravenous conscious sedation (IVCS). IVCS is a minimally depressed level of consciousness that retains the patient's ability to maintain a patent airway independently and continuously and respond appropriately to physical stimulation and verbal commands.

The risks of intravenous conscious sedation include: inhibition of the gag reflex and concomitant risk of aspiration, cardiopulmonary complications (myocardial infarction, cardiac arrhythmias, hypoxemia), and allergic reactions to the sedative or analgesic medications. These risks are small but real; for example, in a prospective study of 14,149 patients undergoing IVCS during upper gastrointestinal endoscopies, the rate of immediate cardiopulmonary events was 2 in 1000. The 30-day mortality was 1 per 2,000 cases. In this study, there was a strong association between lack of monitoring and use of high-dose benzodiazepines with adverse outcomes. There was also an association between the use of local anesthetic sprays to the oropharynx and the development of pneumonia. In order to minimize the risk of intravenous conscious sedation, only qualified personnel will be responsible for conscious sedation. A minimum of two individuals will be involved in the care of patients undergoing conscious sedation-the physician performing the biopsy procedure, and the individual (M.D. or R.N.) who monitors the patients and his/her response to both the sedation and the procedure, and who is capable of assisting with any supportive or resuscitative measures. The room where the procedure utilizing IVCS takes place will have adequate equipment to provide supplemental oxygen, monitor vital signs, and maintain an airway should this be necessary. An emergency cart will also be immediately accessible to the room where the procedure is to take place, and emergency support services will be available on page. Patients will be screened and evaluated for their fitness to undergo conscious sedation by a trained physician. Patients with active cardiac disease are excluded from this study. No local anesthetic spray to the oropharynx will be necessary, given that endoscopy is not a planned procedure. Following the procedure, patients will be observed closely in the recovery room for a minimum of 2 hours.

General Anesthesia

Because of the higher risk of general anesthesia compared with local anesthesia or intravenous conscious sedation, biopsies that would require general anesthesia in order to be performed *are not permitted* on this protocol, unless they are being done for clinical reasons, and excess tissue that otherwise would have been discarded is then banked for the purpose of this

protocol.

9.7.1.5 Shipping of tissue specimens

Specimens in OCT and formalin will be delivered to the Clinical Trials Core Laboratory for storage:

Email the blood bank [redacted] and the current Dana-Farber CRC with the sample information and tracking information the day before shipping specimens.

The core in DMEM will be delivered to the lab of [name] immediately following collection for processing:

Email [name] in the lab [redacted] at least 24 hours before of the procedure. If the biopsy does not yield enough tissue to collect the 5th core, notify the lab that the procedure was performed, but did not yield a core, immediately following the biopsy. The lab will provide 10mL of DMEM in 15mL conical tubes for the collection of specimens, to be stored in a central location.

Coded laboratory specimens will be stored in the Clinical Trial Core Laboratory. These specimens will become the property of DFCI. Participants will be informed that their specimens may be used for research by investigators at DF/HCC and other approved collaborators. Shared specimens will be identified with a sample ID number; all patient identifying material will be removed. Correlative studies described will be performed by [name] in the Department of Cancer Biology at DFCI or relevant core facilities at DFCI.

9.7.1.6 Analysis of tissue specimens obtained from biopsies at baseline and C2D1

Analysis of baseline biopsy

Tumor tissue obtained from the baseline biopsy will be used to examine candidate markers of sensitivity or resistance to abemaciclib therapy, based on available preclinical and clinical data.

- a) DNA: extracted DNA will be subject to whole exome sequencing as an exploratory analysis. Specifically, we will determine copy number for cyclin D1 and cyclin E1/2, and also mutational data for TP53 (approximately 60-80% of TNBCs contain a TP53 mutation). We will determine whether the rate of response is lower in tumors cyclin E amplification, or tumors with TP53 mutations. Exploratory analyses will also be performed to determine other novel predictors of response to abemaciclib.
- b) RNA: extracted RNA will be used to determine expression levels of genes including but not limited to, cyclin D1, cyclin E1, cyclin E2, CDKN2A, CDKN1A, CDKN1B, CDK2, TSC2, and PDK1. In each case, will provide descriptive statistics comparing response rates between tumors with higher or lower levels of expression of these genes.
- c) Protein: Baseline core biopsies will be stained for androgen receptor (AR) and RB. We expect that most, but not all, tumors will be AR-positive. We will determine response rates in patients with AR-positive vs AR-negative tumors. We will also document the concordance rate between RB positivity in archival and metastatic samples.
- d) Fresh tissue: when at least 3-5 cores are obtained from baseline biopsies, 1 will be delivered fresh to the laboratory of [name] (DFCI). The [name] lab team will dissociate this tissue to isolate cancer cells and test novel methods to enhance the efficacy of CDK4/6 inhibition in TNBC cells.

A portion of the baseline biopsy will have RNA extracted. This RNA will then be subjected to analysis of gene expression by Affymetrix microarray and/or using the Nanostring nCounter platform. Tumors will be classified according to published algorithms to determine their individual TNBC subtype. We expect that the majority (but not all) of the RB-positive tumors will fall into the “Luminal Androgen Receptor” or “Mesenchymal Stem Like” subtypes, and as an exploratory analysis will determine if tumors within this subtype have a higher rate of response to abemaciclib. Additionally, in patients who consent, RNA extracted will be used to quantify the expression of several genes, including (but not limited to) those used to classify tumors into PAM50 subtypes[18], those identifying specific TNBC subtypes [19][8], and those that contribute to a signature of RB proficiency or deficiency. This will allow us to depict the landscape of gene expression for all tumors in this study, and also to determine in an exploratory fashion the correlation (or lack thereof) between RB positivity by IHC and “Rb-proficiency” by gene expression. The Nanostring assay will be performed at the BWH Center for Advanced Molecular Diagnostis (CAMD). Some portion of de-identified patient clinical information will be shared with Nanostring Technologies, with patient permission, in exchange for the kits needed to perform this assay.

Analysis of paired baseline and C2D1 biopsies

- a) Phospho-RB: FFPE tissue from baseline and C2D1 biopsies will be stained for p-RB (ser780) using protocols established at the Brigham and Women’s Hospital. Sections will be scored manually and the percentage of positive tumor cells will be recorded – a minimum of 200 cells will be counted. A tumor H score will be calculated. We will determine whether (i) baseline RB phosphorylation level predicts response to abemaciclib and (ii) whether suppression of RB phosphorylation after commencement of therapy is associated with an increased response rate.

- b) FFPE tissue from baseline and C2D1 biopsies will be stained for proteins involved in the regulation of cell proliferation in the lab of [name], PhD at Dana-Farber Cancer Institute.

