1.4 Exploratory objectives

To explore additional potential biomarkers in blood and tumor tissue samples that might predict response or resistance to abemaciclib.

To determine the association between genomic alterations in tumor DNA (mutations, copy number alterations, mutational burden) and RB expression and other tissue biomarkers by immunohistochemistry as well as response to abemaciclib.

To determine if there are any changes in the T-cell phenotype during exposure to abemaciclib.

To explore changes in the microbiome induced by therapy comparing stool samples collected at

baseline, during treatment, and at the time of progression. Changes in microbiome will be compared to other trial endpoints.

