13.2 Sample Size, Accrual Rate and Study Duration

This is a single-arm, two-stage phase 2 study in order to determine the efficacy of abemaciclib monotherapy in patients with metastatic RB-positive TNBC. There is no data for response to abemaciclib in patients with TNBC who are RB-positive. A response rate of 20% would be of clinical interest. A true response rate of 5% would not be of clinical interest. We have used a Simon optimal two-stage model with a one-sided type I error of 10% and type II error of 0.1 (90% power) to detect the difference between null (5%) and alternative (20%) objective response rates. The first stage of the study includes 12 patients with metastatic triple-negative breast cancer which is RB-positive. As of June 2018, it was discovered that a participant without measurable disease was registered and treated on this trial. As such, this participant is considered unevaluable in relation to the primary endpoint. Therefore, we plan to enroll a total of 13 participants to the first stage, with the expectation that 12 will be evaluable for response. The statistical plan will otherwise remain unchanged. If in the first stage there is at least one

response, accrual will continue to the second stage where an additional 25 patients will be enrolled. If there are at least 4 responses among the 37 evaluable patients, the regimen would be considered to be of clinical benefit worthy of further study (exact $\alpha=0.09$). If the true the response rate is 5%, the probability that the study would discontinue after stage I is 54%. The total accrual to the study will be 38 given the additional patient added for evaluation in the first stage.

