13.5 Analysis of Exploratory Endpoints

Descriptive statistics will be used to characterize any types of biomarkers discovered in correlative work, T-cell phenotypes via serial PBMCs blood draws (prior to receiving therapy, while on therapy, and at the time of progression), any changes in the serial microbiome collection, and its correlation with participant outcomes.

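### Gene expression is to be compared with response in higher and lower groups with no stated cut and no continuous summary, which loses information in a small exploratory dataset

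*Combined protocol and SAP*

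**What the plan says.** Section 9.7.1.6(b) names "cyclin D1, cyclin E1, cyclin E2, CDKN2A, CDKN1A, CDKN1B, CDK2, TSC2, and PDK1" and leaves the list open. For each gene the team "will provide descriptive statistics comparing response rates between tumors with higher or lower levels of expression of these genes". The same section says expression will be measured by Affymetrix microarray and/or Nanostring, which are quantitative platforms. It does not say where higher ends and lower begins.

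The purpose is set in section 1.4: "To explore additional potential biomarkers in blood and tumor tissue samples that might predict response or resistance to abemaciclib". Section 13.5 adds only this: "Descriptive statistics will be used to characterize any types of biomarkers discovered in correlative work". No test, alpha or power attaches to gene expression. Section 2.4 states that, apart from RB, no marker has been validated for predicting response or resistance to this drug class in breast cancer, so the documents supply no external threshold.

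Section 13.4 treats a different marker differently. Quantitative phospho-Rb reduction is to be modelled by logistic regression, with 89% power quoted for an odds ratio of 4.0 per standardised unit at a 20% overall response rate.

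**The concern.** Expression is measured on a continuous scale, but the one stated comparison with response reduces it to two groups. That has two consequences. First, patients just above and just below the cut are treated as different, while patients far apart on the same side are treated as alike, so information is lost. Second, with the cut unstated, it can be set separately for each of nine or more genes after responses are known, and a reader could not tell whether a reported contrast came from the biology or from the cut.

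The plan's own RB assay shows how much a grouping can depend on its cut. In section 2.1, moving the threshold from >10% to >50% changed positivity in the first 18 pre-screened patients from 94% to 72%. That change was prompted by staining rates, not by responses.

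At stake is how much can be learned about predictors of sensitivity and resistance from tissue obtained largely by research biopsy.

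**Working it through.** **Inputs.** From section 13.2: "A response rate of 20% would be of clinical interest"; "A true response rate of 5% would not be of clinical interest"; and the final rule, "If there are at least 4 responses among the 37 evaluable patients". From section 13.4: 33 evaluable biopsy pairs, OR 4.0 per SD, two-sided 0.05 (stated for the Fisher test, assumed here for the logistic model). The 33 pairs are a proxy for usable baseline RNA samples, for which no number is given.

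**1. Reproducing the plan's figures.**
- Early stopping at a 5% response rate is the chance of no response in 12 patients: 0.95^12 = 0.540. Section 13.2 says "the probability that the study would discontinue after stage I is 54" per cent. It agrees.
- Logistic power is Φ(√(N·P·(1−P))·ln OR − 1.96). With N = 33, P = 0.20, OR = 4: √5.28 = 2.298; 2.298 × 1.386 = 3.185; Φ(3.185 − 1.96) = Φ(1.225) = 0.890. The stated 89% is reproduced.

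**2. Number of responders.**
- At 20%: 0.20 × 37 = 7.4; 0.20 × 33 = 6.6.
- At an illustrative 10%: 0.10 × 37 = 3.7.
- At the 5% null: 0.05 × 37 = 1.9, and then only if the trial passes stage 1.

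**3. Information kept by a split.** For a normal predictor with a modest association, cut so that a fraction q lies above, efficiency is φ(z)²/(q(1−q)), where z is the normal quantile at 1−q.

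| Cut (upper fraction) | Efficiency | Loss |
|---|---|---|
| 1/2 | 0.637 (= 2/π) | 36% |
| 0.40 | 0.622 | 38% |
| 1/3 | 0.595 | 41% |
| 1/4 | 0.539 | 46% |
| 1/5 | 0.490 | 51% |

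The median is the most favourable cut. Even there, 37 patients carry the information of 37 × 0.637 = 23.6.

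**4. The same loss in the plan's own power formula.** Multiplying the information by 0.637: √(5.28 × 0.637) × 1.386 − 1.96 = 0.58; Φ(0.58) = 0.72. So the 89% quoted for a quantitative marker would be about 72% for the same marker split at its median. The 2/π rule is exact only for weak associations, so at OR 4 this is approximate.

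**5. Simulation check** (4,000 runs per setting; normal predictor, linear logit, 20% response, two-sided 0.05). The protocol plans none of these tests on RNA data, so the figures only illustrate the efficiency gap.

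| Setting | Continuous logistic (LR) | Rank-sum | Median split, Fisher |
|---|---|---|---|
| N = 33, OR 4 | 77% | 70% | 47% |
| N = 37, OR 4 | 81% | 76% | 54% |
| N = 37, OR 2 | 36% | 31% | 20% |

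Part of the gap is Fisher's conservatism: its null rejection rate at N = 33 was 3.0%, against 4.3% for rank-sum. A score test on the continuous scale against an uncorrected chi-square on the split have nearly equal null rates (4.7% and 4.8%). At N = 33 and OR 4 they give 74% and 51%, so most of the gap remains. The Fisher figure is also unstable: with an odd N, putting the middle sample in the other group lowers 47% to about 36–37%.

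**The case against.** The strongest reply is that this comparison is exploratory and descriptive. Sections 1.4, 9.7.1.6(b) and 13.5 all say so. There is no significance filter through which a predictor could be missed, and the power figures above compare tests that nobody plans to run. That stands, and it sets the weight of the point.

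Three stronger readings are tempting, and the documents do not support them.
- A reader might infer that tumors will be split into halves. Neither a median nor equal groups is mentioned, so the 36% loss is the best case under normality, not a description of the plan.
- A reader might take about 7 responders as the forecast. The 20% rate is the alternative of interest, not a prediction. At the 5% null about 2 of 37 would respond.
- A reader might conclude that the trial loses power. No stated power or error rate involves these genes.

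Nor would a continuous analysis rescue the question. With 7 responders and 30 non-responders, the approximate 95% half-width of an AUC near 0.5 is 1.96 × √(38/(12 × 7 × 30)) = 0.24. Nine independent null comparisons at 0.05 would give a 1 − 0.95^9 = 37% chance of at least one false positive. Both limits apply whichever summary is used.

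Finally, the text does not forbid continuous summaries, and descriptive statistics could include them. But none is stated for expression against response, while section 13.4 does state one for phospho-Rb.

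**Conclusion.** The point holds as a minor improvement. The only stated comparison of gene expression with response groups a quantitative measure at an unspecified cut. For a normal predictor on a log scale the loss is about 36% at best and grows with unequal cuts (46% at one quarter). The missing cut is at least as important as the loss, because it leaves the grouping open to choice after responses are seen. The number of responders makes both matter more: about 7 in 33 to 37 patients if the 20% rate is reached, fewer otherwise.

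No trial decision, stated error rate or stated power changes, and any finding remains hypothesis-generating. The size rests on normality, a linear logit and 33 biopsy pairs standing in for RNA samples. The direction does not depend on the exact sample number.

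**What to change.** In section 9.7.1.6(b), with a reference in section 13.5, replace the higher/lower comparison with wording such as:

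*Each gene will be summarised on its continuous, platform-normalised log scale. Its association with objective response and with disease control will be reported as a rank-based area under the ROC curve, or as a logistic odds ratio per SD, with a 95% confidence interval. Any high/low display will use the median, fixed in advance, and is for illustration only. All results are hypothesis-generating.*

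The odds ratio per SD matches what section 13.4 already does for phospho-Rb; either estimate serves, but one should be chosen before responses are examined. Platform normalisation needs saying because the protocol allows either or both assays. Disease control adds events: at the 34% rate anticipated in section 13.4, 0.34 × 33 = 11.2.

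The cost is protocol wording and a little programming, with the same samples and assays. The one downside is that an AUC or odds ratio is slightly less intuitive than two response rates, which can still be shown beside it.

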9.8 Research Stool Collection

9.8.1 Collection

All stool samples will be collected by each patient at home using a home-based, self-collection and mail method for stool that has been proven to provide nearly equivalent metagenomic and metatranscriptomic data to state-of-the-art fresh-frozen sample-collection protocol.

Patient questionnaires are included in the kits. The questionnaires should be completed at the time of stool collection and mailed back along with the sample. Stool samples and questionnaires that are not collected at the protocol-specified collection time points will not be protocol violations.

Given that this procedure was added to the study mid-way through accrual, only new participants will be approached to participant in this correlative study. If a patient doesn't complete a baseline collection, the series may not continue as this collection is essential to analysis.

9.8.2 Handling and shipping of stool specimens

All kits will be provided to the patients at a clinic visit or will be mailed to their home address. Patients will also be provided with a mailer in which to return the sample. All samples will be shipped by the patient at ambient temperature to the Breast Tumor Immunology Lab (BTIL, [name], PhD) where they will be processed and stored until batch shipment for analysis.

9.8.3 Analysis

We will quantify microbiome features from amplicon, metagenome, metatranscriptome using established pipelines to identify strain-level taxonomic, functional gene, transcriptional, and microbially-mediated metabolite profiles associated with patients with Rb+ TNBC treated with abemaciclib.

